### **Noncompliance**

All patients will be evaluated based on an intention-to-treat analysis. If there is noncompliance to the medicine home taper course indicating cross-over from the treatment arm to the control arm, the overall dose of glucocorticoid will be noted, and patients will be analyzed in their original randomization arm.

### **Unmasking**

Unmasking of the treatment arm will occur should emergency medical services be required within the first 6 days after surgery and emergency personnel need to access a full medicine list for the study patient.

## **7.0 Risks**

### **Side effects that can come from taking Dexamethasone or Methylprednisolone:**

- upset stomach
- stomach irritation
- vomiting
- headache

- dizziness
- insomnia
- restlessness
- depression
- anxiety
- acne
- increased hair growth
- easy bruising
- irregular or absent menstrual periods
- skin rash
- swollen face, lower legs, or ankles
- vision problems
- cold or infection that lasts a long time
- muscle weakness
- black or tarry stool

**Breach of Confidentiality Risk:**

Because patient data is being collected there is a slight risk of a breach of confidentiality. During this study every attempt will be made to keep the patient's protected health information (PHI) private. Most study data will be maintained in a Vanderbilt REDCap database. Vanderbilt Redcap is a secure, web-based application for building and managing online databases. The data obtained and stored in Redcap will only be accessible by research personnel. Any data sent to non-key study personnel for statistical analysis will be de-identified (dates will be shifted using a Redcap feature).

Project team members listed as Key Study Personnel with existing electronic health record (EHR) system access rights may also be granted use of REDCap Clinical Data Interoperability Services (CDIS) tools. These tools are designed to enable transfer of relevant study-related data from the Vanderbilt Research Derivative and/or directly from the EHR into REDCap. Any physical study forms (ex. consent documents, surveys) will be kept in a locked cabinet in the principal investigator's office]. All study data will be maintained for 6 years following study completion. Following this 6-year period, the Redcap database will be archived, and all physical study forms will be disposed of in shred-it confidentiality bins.

**Benefits**

We hope to determine if post-operative range of motion can be improved by peri-operative use of Dexamethasone.

**8.0 Reporting of Adverse Events or Unanticipated Problems involving Risk to Participants or Others**

All adverse events related to this study (breach of confidentiality or drug adverse event) should be reported to the principal investigator immediately. The principal investigator will then ensure prompt reporting to the IRB based on policy number III.L.

## **9.0 Study Withdrawal/Discontinuation**

### **Participant Withdrawal**

Participation in this study is voluntary. If at any time a study participant wishes to be withdrawn from the study, they may do so by contacting their treating physician, the principal investigator or the research coordinator and letting them know they withdraw their consent. The date in which the participant withdraws their consent will be noted in their study file.

### **Safety Monitor**

The Principal Investigator will designate a Safety Monitor for this study. The Safety Monitor will not be involved in the study work and will work independently of the Principal Investigator. The Safety Monitor will be provided reports by the statistician every 6 months, from first subject enrollment, and make a determination on the continuance of the study based on reports of adverse events and protocol deviations.

## **10.0 Statistical Considerations**

### **Sample Size Justification**

Prior studies suggest Flexion/extension arc after intra-articular fracture  $\sim 105^\circ$ . Difference suggested by prior retrospective study with dexamethasone shows potential improvement ( $\delta$ ) of  $27^\circ$  (avg post-operative AROM  $132.5^\circ$ ). Conservatively, will attempt to see an improvement of  $25^\circ$  ( $\delta$ ). Average standard deviation from literature of post-operative intra-articular elbow fractures range of motion is  $17^\circ$  ( $\sigma$ ). A total of 22 patients are needed (11 treatment and 11 control) to be able to reject the null hypothesis with 90% power and  $\alpha = 0.05$ . Assuming a 20% loss to follow-up based on prior studies ( $\sim 10\%$ ) + non-compliance of six-day home taper course. As we are stratifying our treatment and control groups based on fracture type, we will need 18 patients in each treatment arm for each fracture and 18 patients in each control arm.

### **Statistical Analysis**

- a. Primary analysis
  - i. Intention-to-treat
  - ii. Baseline characteristics between treatment arms will be compared using univariate descriptive statistics.
  - iii. Primary end-point (range of motion: continuous variable) → Univariate analysis of unmatched, interval variable with two groups assuming non-normal distribution: Mann-Whitney U Test will be performed.

- iv. Secondary end-points that are dichotomous (infection, revision surgery, heterotopic ossification, and other complication) will be analyzed with a chi-square or Fisher's exact test where the assumptions for a chi-square test are not met.
- v. Secondary end-points that are nominal or ordinal (Pain score, DASH score) will be analyzed using a Mann-Whitney U Test.

b. Subgroup analysis

- i. Analysis will be performed based on fracture type and stratification will make comparison possible.
- ii. Multivariate analysis using linear regression for the interval variable (range of motion) will be performed based on:
  1. Age <65 vs Age >65
  2. Mechanism of injury (High-energy vs. Low-energy)
  3. Treatment type
  4. Time from injury to surgery

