### **Enrollment Goal**

We will seek to enroll 18 patients in each treatment arm per fracture type and 18 patients in each control arm, for a total of 144 patients.

Fracture Type	Treatment Arm	Control Arm	Total
Distal humerus fracture	18	18	36
Radial head	18	18	36
Proximal ulna	18	18	36
Combined	18	18	36
			144

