### **Randomization**

Patients will be randomized according to a stratified permuted block randomization with a block size of 4. Randomization will be stratified based on fracture type: radial head, distal humerus, proximal ulna, combined. Treatment A will receive glucocorticoid and Treatment B will receive placebo. There will be 9 total blocks per fracture type, for 36 patients in each fracture-type strata and an even balance in all 4 strata, for 18 in each treatment arm.

Randomization will take place after consent. A randomization allocation table will be uploaded into REDCap. Randomization will be conducted by an Orthopaedic research coordinator. The treating physician, study research coordinator and patient will be blinded to the treatment assignment.

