Statistical Analysis Plan (SAP)

Steroid Administration for Articular Fractures of the Elbow (SAFE Trial): A Randomized, Controlled Trial of Perioperative Glucocorticoids during Treatment of Intraarticular Elbow Fractures

Principal Investigator: [name]

Assistant Professor, Orthopaedic Surgery

Protocol Identification Number: 210125

Clinicaltrials.gov Identifier: NCT04738318

Version Date 03/09/2021

Statistical analysis plan

Demographics will be compared between each treatment arm in each stratification group for comparison and summary statistics for each treatment arm will be provided. If significant differences exist in patient, injury, or treatment variables, subgroup analysis will be performed. Assumptions for each variable will be assessed for normality using histograms and frequencies and cross tabulation will be tabulated for categorical and ordinal variables. If continuous data is not normally distributed, we will use non-parametric analysis methods. Graphical methods will be used to examine data distributions, identify influential observations, and perform transformations if needed. Prior to hypothesis testing, the data will be screened for errors and missing values using descriptive statistics and histograms. Suspicious values will be confirmed for accuracy and changes will be documented in an appendix. Every effort will be made to minimize missing or incomplete data. Study personnel will follow-up with all providers and patients to collect data. Data will be analyzed in a pragmatic fashion and all collected data will be analyzed.

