We will use the open-source statistical package R (R Development Core Team, 2012) and Stata 16 statistical software (StataCorp LLC, 2019, College Station, TX) for analysis. An intention-to-treat analysis will be conducted including all eligible patients as originally randomized. Analysis of each primary and secondary endpoint will be performed with all patients at each follow-up time point. Interactions for fracture-type and treatment group will be modeled at each follow-up time point and if significant, each fracture-type group will be independently analyzed. Multivariable proportional odds models for the Aim 1 dependent variable, range-of-motion, will be performed and multivariable logistic regressions will be performed for Aim 2 outcomes evaluating complications and safety. The Aim 3 dependent variable is continuous MME total and will be analyzed using a multivariable proportional odds model as the total amount consumed for each patient during the post-operative course.

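### The SAP neither restates nor ranks the protocol's primary test of range of motion, and that test leaves out fracture type, the only randomisation stratum

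*Protocol*

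**What the plan says.** **Protocol, 10.0 Statistical Analysis.** Under the primary analysis heading, item a.iii gives range of motion "Univariate analysis of unmatched, interval variable with two groups assuming non-normal distribution: Mann-Whitney U Test will be performed". This is a two-group comparison with no stratum and no covariate. Fracture type appears under subgroup analysis (b.i). The linear regression listed there (b.ii) does not include it.

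**Protocol, 5.0 Randomization.** "Randomization will be stratified based on fracture type: radial head, distal humerus, proximal ulna, combined". No other stratification factor is named.

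**SAP.** "Multivariable proportional odds models for the Aim 1 dependent variable, range-of-motion, will be performed". No covariates are listed, the models are not called primary or supportive, and the Mann-Whitney test is not mentioned. Endpoints are to be analysed in all patients at each visit. Fracture type appears in the comparison of baseline data by stratum and in an interaction step: "Interactions for fracture-type and treatment group will be modeled at each follow-up time point and if significant", each type is then analysed separately. A general rule adds: "If continuous data is not normally distributed, we will use non-parametric analysis methods".

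No sentence in the sections available ranks the SAP's model against the protocol's test. Title and signature pages were not available, so a ranking there cannot be excluded.

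**The concern.** Two methods are planned for one endpoint and they answer somewhat different questions: one compares ranks between arms, the other gives an adjusted odds ratio. The SAP is where a reader expects the analysis to be fixed, yet it passes over the protocol's primary test and describes another method with open covariates. Its normality rule sits badly with the protocol, which assumes non-normality outright. Read literally, the rule would let the Mann-Whitney test be dropped if the data looked normal.

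The second part concerns the stratum. Stratified randomisation balances fracture type between the arms, so differences between types add nothing to the error of the treatment comparison. An unstratified test still counts those differences as noise. If types differ in mean motion, the test is stricter than its nominal 5% and gives up power for moderate effects. The SAP does not say whether fracture type stays in its model when the interaction is not significant, so its interaction step does not settle the matter.

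**Working it through.** **1. The plan's own figure.** Protocol 10.0, Sample Size Justification: difference 25 degrees, SD 17, 90% power, alpha 0.05, 11 per arm. Sidedness is not stated. A two-sided two-sample t-test (noncentral t) gives 87.5% power at 10 per arm and 90.6% at 11, so 11 per arm is reproduced.

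**2. Inputs for the check.**
- From the protocol: four fracture types, 18 per arm per type, 20% loss. 18 × 0.8 = 14.4, taken as 14 evaluable, or 4 × 14 = 56 per arm.
- Assumed, not in the documents: type means evenly spaced over a range R of 0, 15, 20 or 30 degrees; normal data; a true effect of 10 degrees, to show a moderate benefit; two-sided 0.05.
- The protocol does not say whether SD 17 is within or across fracture types. The main run takes it as within.

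**3. Hand approximation of the size of the unstratified test.** Four evenly spaced means have between-type SD b = R√5/6. The arm difference varies with the within-type SD of 17, but the unstratified test scales it by √(17² + b²). The effective critical value is therefore 1.96 × √(17² + b²)/17.

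| R | b | Total SD | Effective critical value | Approximate type I error |
|---|---|---|---|---|
| 0 | 0 | 17.00 | 1.960 | 5.0% |
| 15 | 5.59 | 17.90 | 2.063 | 3.9% |
| 20 | 7.45 | 18.56 | 2.140 | 3.2% |
| 30 | 11.18 | 20.35 | 2.346 | 1.9% |

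**4. Simulation.** 20,000 trials per setting, outcome rounded to 1 degree; unstratified Mann-Whitney against van Elteren (Mann-Whitney stratified by fracture type).

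| R | Type I, unstratified | Type I, stratified | Power at 10°, unstratified | Power at 10°, stratified |
|---|---|---|---|---|
| 0 | 5.2% | 5.1% | 85.2% | 84.4% |
| 15 | 3.7% | 4.8% | 82.8% | 84.5% |
| 20 | 3.3% | 5.1% | 80.6% | 84.5% |
| 30 | 1.8% | 5.0% | 73.4% | 84.4% |

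The type I column agrees with step 3. Separate repeat runs gave 1.6 to 2.2% type I error and about 74% power for the unstratified test at R = 30.

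**5. At the planned effect.** The standard error of the arm difference is 17 × √(2/56) = 3.21, and 25/3.21 = 7.78. That lies far above even the strictest critical value of 2.346. In simulation both tests had 100% power at 25 degrees, and they never disagreed in 3,000 trials at each of R = 0, 15 and 30.

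**6. If SD 17 is across fracture types.** At R = 15/20/30, type I error of the unstratified test is 3.7/3.1/0.8%, and power at 10 degrees is 86/88/90% against 88/91/98% stratified. The direction is the same.

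**7. Does the choice between the two documents' methods matter?** With SD 17 within types and a 10-degree effect, the Mann-Whitney test and a proportional odds model with treatment and fracture type fall on opposite sides of p = 0.05 in 1.7/4.5/6.5/14.6% of trials at R = 0/15/20/30 (2,500 trials each). With treatment as the model's only term they disagree in at most 0.6%. Most of the disagreement therefore comes from whether fracture type is in the analysis. With no treatment effect, rejecting if either method rejects adds at most 0.14 points to the type I error of the fracture-type model alone (5,000 trials each).

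**The case against.** The best defence is that only one test of range of motion stands under a primary analysis heading, the protocol's Mann-Whitney test. On that reading the SAP's model is its adjusted companion, much as the protocol itself places a regression beside the test. This stands in part. A reader might infer that the SAP names a rival primary analysis; it does not. What remains is that the SAP neither confirms the protocol's test nor gives its own model a status.

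Second, an unstratified test after stratified randomisation is valid. This stands. A reader might infer inflated false positives or a trial left underpowered. The results show neither: the error goes the conservative way, and every power loss above needs an effect well below 25 degrees and a spread that the documents do not give. Nor does picking between the Mann-Whitney test and the fracture-type model add materially to type I error. Free choice among unlisted covariates could, but that has not been quantified here.

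Third, the trial is sized by fracture type ("We will seek to enroll 18 patients in each treatment arm per fracture type and 18 patients in each control arm"), and stratification is irrelevant within one type. This is true at that level. But the protocol's primary test is written for two groups, and the SAP uses all patients, separating types only after a significant interaction. The main comparison as written is pooled.

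**Conclusion.** The point holds as a gap in specification with a modest statistical cost, and it should be fixed. The textual part needs no assumptions: the protocol names one primary test, and the SAP describes another method for the same endpoint without status or covariates, alongside a normality rule that could displace the protocol's test.

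The stratum part rests on the assumed spread between fracture types. Unstratified, the test's type I error falls from about 5% to about 4, 3 and 2% at spreads of 15, 20 and 30 degrees. Power for a 10-degree effect is about 2, 4 and 11 points below the stratified test. There is no loss at the planned 25 degrees or within a single fracture type.

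**What to change.** - State in both documents that one analysis of range of motion is primary, and stratify it by fracture type as randomised (four levels). The van Elteren test keeps the protocol's rank-based approach and held its 5% level in simulation.
- State that the SAP's normality rule does not choose the primary test.
- Label the SAP's proportional odds model supportive, and list fracture type and every other covariate in advance.
- If the sponsor prefers that model as primary, the same covariate list is needed. In the simulations its Wald test with fracture type ran slightly above nominal, at 5.2 to 6.2%.

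The cost is wording in two documents. No patients, visits or data are added, because fracture type is already recorded for randomisation. The statistical downside of stratifying is at most about 1 point of power if fracture types do not differ (84.4% against 85.2% for a 10-degree effect).

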### **4.0 Inclusion/Exclusion Criteria**

#### **Inclusion Criteria**

- All adults  $\geq 18$  years old with an intra-articular traumatic elbow fracture to be treated with operative intervention and a standardized post-operative rehab protocol
  - Intra-articular elbow fracture defined as:
    - Distal humerus
    - Proximal ulna
    - Radial head fracture
    - Combination fracture of two or more of the above
  - Radiographs present confirming intra-articular injury

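### The secondary regression for range of motion splits age at 65 without assigning patients aged 65 and discards part of the age information; age in years would be better

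*Protocol*

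**What the plan says.** Protocol section 10.0, Statistical Analysis, has two parts. Part a sets the primary comparison of range of motion as an unadjusted two-group test: "Mann-Whitney U Test will be performed". Part b, on subgroups, adds a regression: "Multivariate analysis using linear regression for the interval variable (range of motion) will be performed based on" four items, namely age, mechanism of injury, treatment type, and time from injury to surgery. The age item reads "Age <65 vs Age >65". No reason is given for the cut, and no expected age distribution appears in either document.

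The inclusion criteria (Protocol 4.0) admit adults aged 18 or over "with an intra-articular traumatic elbow fracture to be treated with operative intervention and a standardized post-operative rehab protocol", with no upper age limit. The enrollment goal (Protocol 5.0) is 18 per arm in each fracture type, "for a total of 144 patients".

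The SAP names a different model for the same outcome: "Multivariable proportional odds models for the Aim 1 dependent variable, range-of-motion, will be performed". It lists no covariates and no coding of age, so it neither repeats nor corrects the split. It does undertake to analyse all the data collected, and to keep every eligible patient in the arm to which they were randomised.

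**The concern.** Two things are wrong with the age item.

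- **A gap.** A patient recorded as 65 is in neither group. Software given those two definitions literally would return a missing value, and a complete-case regression would drop the patient. Otherwise the analyst must decide after the data are in where such patients go.
- **A loss of information.** Replacing age by two groups assumes that range of motion does not vary with age from 18 to 64, jumps at 65, and does not vary after that. If the true relation is gradual, the two-level term removes less residual variation than age in years would.

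At stake are the completeness and precision of the secondary adjusted analysis, and the quality of its adjustment for age.

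**Working it through.** **Does age enter the main design?** The documents give no figure for age. The only related figure that can be reproduced is the sample size. With a difference of 25°, an SD of 17° and two-sided alpha of 0.05, the t-test has power 0.875 at 10 per arm and 0.906 at 11 per arm. So 11 per arm (22 in total) is reproduced for 90% power, without using age. The randomisation is stratified by fracture type only, and the primary test is unadjusted.

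**How many patients fall in the gap?** The age distribution is an assumption, because the documents give none. Take ages as normal, truncated to 18–95, with mean 40 to 65 and SD 15 to 20, and age recorded in whole years. With q = P(65 ≤ age < 66), the expected number is 144 × q and the chance of at least one is 1 − (1 − q)^144.

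| Assumed mean, SD | q | Expected of 144 | Chance of at least one |
|---|---|---|---|
| 40, 15 | 0.0068 | 0.97 | 62% |
| 50, 18 | 0.0160 | 2.30 | 90% |
| 65, 15 | 0.0272 | 3.92 | 98% |

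The whole grid gives about 1 to 4 patients.

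**How much age information does the split lose?** If the effect of age is linear, the share kept is the squared correlation between age and the two-level indicator. With p the share above the cut:

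- normal ages: kept = φ(z)² / [p(1 − p)], where z is the normal quantile at 1 − p;
- uniform ages: kept = 3p(1 − p).

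| Share above 65 | Loss, normal | Loss, uniform |
|---|---|---|
| 50% | 36% | 25% |
| 30% | 42% | 37% |
| 20% | 51% | 52% |
| 10% | 66% | 73% |
| 5% | 78% | 86% |

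The last uniform entry is set aside: uniform ages starting at 18 with 5% above 65 would have to stop at 18 + 47/0.95 = 67.5 years. That leaves about 25% to 78%. The 25% end needs uniform ages with their median at 65. For the truncated normal ages the loss is 33% to 54% with mean 50–65, and 49% to 74% with mean 40–45. If the true effect is a step at 65, the loss is zero.

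**What does that do to the treatment estimate?** Assume that the regression contains the randomised arm, which is unrelated to age by design. Let age explain a share R² of the variance in range of motion, and let the split keep a fraction k of that. Relative to age in years, the standard error of the treatment effect is multiplied by √[(1 − kR²)/(1 − R²)].

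- R² = 0.05, k = 0.55: √(0.9725/0.95) = 1.012.
- R² = 0.10, k = 0.55: √(0.945/0.90) = 1.025.
- Lower end of the loss range, R² = 0.05, k = 0.75: √(0.9625/0.95) = 1.007.
- Upper end, R² = 0.10, k = 0.22: √(0.978/0.90) = 1.042.

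The R² values are assumptions; neither document relates age to range of motion.

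**The case against.** The strongest reply is that this is loose notation and little more. The SAP's undertakings to use all data and all randomised patients make a slip for 65 and over (or 65 and under) the likelier reading, and a statistician honouring them would place the 65-year-olds somewhere. If age were computed to the day from dates, almost nobody would be exactly 65 and the gap would nearly vanish; the documents do not say how age is held. The item also sits under subgroup analysis, where a two-level age group is a common way to present results. All of this stands, and it limits the point. It does not remove it: the boundary is unassigned in the only place where age is coded, and the item is a term in a regression, where two levels are not needed.

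Three stronger readings are tempting, and the documents do not support them.

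- **That 65-year-olds will be excluded.** No rule says so, and the SAP points the other way. Loss of these patients is a risk of literal coding.
- **That the split loses a fixed share, such as a third to a half.** That holds for roughly normal ages, a linear effect and about 20% to 50% of patients above 65. The documents establish none of these.
- **That the trial's main result is weakened.** The primary test, the randomisation and the sample size do not involve age.

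**Conclusion.** The point holds as a minor one. The age groups leave 65 unassigned, and nothing in the protocol or SAP repairs this. About 1 to 4 of 144 patients are affected, if age is held in whole years and follows the assumed distributions. Splitting age discards about 25% to 78% of a linear age effect under assumed distributions, and none of a step effect at 65. For the treatment comparison in the secondary linear regression, this means a standard error about 1% to 2.5% larger if age explains 5% to 10% of the variance and 55% of that is kept, or 0.7% to 4.2% over the whole loss range. The SAP's proportional odds model is affected only if it adopts the same coding, which it does not state.

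**What to change.** - In Protocol section 10.0, replace the two age groups in the regression with age in years as a continuous covariate, with a restricted cubic spline or a pre-specified check of linearity.
- In the SAP, list the covariates of the proportional odds model and their coding. If age is among them, code it the same way.
- If an age subgroup is wanted for description, define it as under 65 versus 65 and over. Closing the boundary alone would cure the gap but not the loss of information.

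The cost is about one line in each document. Demographics are already imported from the health record (Protocol 6.0, Enrollment Visit), so no new data are needed, and the 144 patients, the primary test and the randomisation stay as they are. There is a modest statistical price: a linear term assumes a straight-line effect across all adult ages, and a spline that relaxes this costs one or two degrees of freedom. The change should be made before the data are analysed, so that the coding cannot depend on the results.
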